The web-based Survivorship Care Plan in Reproductive Health (SCP-R) intervention was developed to address unmet informational and clinical management needs for hot flashes, fertility-related concerns, contraception, and sexual health in YBCS. Research findings, professional society guidelines and clinical expertise on these reproductive health issues were curated into screening and management strategies that will be delivered to YBCS and their HCPs via the SCP-R intervention. A web-based intervention and text message support were chosen to enhance intervention accessibility.

This report details the design, recruitment, and baseline characteristics of YBCS and HCP participants of the randomized controlled trial testing the efficacy of the SCP-R intervention on improving reproductive health in YBCS. We hypothesize that YBCS who receive the SCP-R intervention will be more likely to improve on at least one of four targeted reproductive health outcomes (hot flashes, fertility-related concerns, sexual health, and contraception) compared to waitlist controls.

Material and Methods

The SCP-R trial will test the efficacy of a 24-week, web-based educational intervention with text message support in improving reproductive health issues experienced by female YBCS.

Following online eligibility screening and consent, YBCS complete an enrollment questionnaire and undergo a 7-day run-in period for reporting daily hot flash frequency and severity via text messaging. Adherent participants are randomized in a 1:1 ratio to the intervention or waitlist control arm. Participants in the intervention arm receive access to the full web-based SCP-R intervention and reproductive health text message prompts, while participants in the waitlist control arm receive access to a list of curated web-based resources and study adherence text messages. All participants will be followed for 24 weeks, report daily hot flash frequency and severity via text messaging, and complete a 12-week and a final 24-week questionnaire.

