The final SCP-R intervention included four sections for each of the four planned reproductive health issue (hot flashes, fertility-related concerns, vaginal symptoms and contraception) and an additional fifth issue on genetic cancer risk. For each issue, the four sections included: 1) a 1- to 2-page SCP framed in a question and answer format; 2) a detailed summary of the systematic review results with hyperlinks to primary research articles; 3) a summary of clinical guidelines with hyperlinks; 4) a list of curated web-based resources. This content was programmed into the study website. The intervention arm will be able to access all 4 sections for all 5 issues (Appendix A); the waitlist control arm will only be able to access the list of curated web-based resources for all 5 issues.

Website and text messaging platforms

We collaborated with an experienced web architect to develop a HIPAA-compliant website that enabled online participant registration, consent, completion of questionnaires, automated randomization and access to group-specific intervention material, integration with MOSIO, a text messaging software, and pairing of YBCSs with their nominated HCPs. The web portal is programmed to send study gift cards and weekly reminders on incomplete tasks to YBCS and HCP participants.

The text messaging platform is programmed to push daily text messages to all YBCS participants to ascertain hot flash frequency and severity. Natural language processing is embedded to minimize variation in how participants provide hot flash responses. In addition, biweekly text messages with reproductive health prompts will be sent to YBCS participants in the intervention arm, while biweekly study adherence text messages will be sent to YBCS participants in the waitlist control arm. The text messaging platform supports opt out by participants and two-way text messaging capabilities between participants and study staff.

This web- and text message-based design supports streamlined YBCS screening, consent, follow-up, and data collection, enables geographically diverse recruitment and utilizes fewer resources compared to a traditional in-person RCTs. Daily hot flash text messages will provide near real-time data collection to minimize recall bias.

YBCS eligibility, recruitment, consent and enrollment

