Contraception outcomes will be analyzed in participants at risk of unintended pregnancy, defined as having a uterus and at least one ovary, sexually active in the 24 months prior to or during the study, ≤ 45 years old. For the primary analysis, use of highly effective birth control methods (intrauterine devices, female sterilization, male partner sterilization, combined hormonal contraception, progestin implants or injections) during follow up will be considered an improvement for the primary composite outcome. Secondary contraceptive outcomes will include confidence to talk with a HCP about contraception, plans to implement and implementation of suggestions from the contraception SCP.

Sexual health will be measured the Vaginal Atrophy Symptoms Score, a 4-item scale on vaginal dryness, soreness, irritation and dyspareunia experienced in the prior 4 weeks [29]. Each item has a 4-point Likert scale response (0-none, 1-mild, 2-moderate, 3-severe). The scale will be summarized by averaging responses, with higher scores indicating a greater level of vaginal atrophy. For the primary analysis, a decrease of 50% in the score will be defined as an improvement in vaginal symptoms for the primary composite outcome. Secondary outcomes included sexual desire, arousal, orgasm and pain via the 19-item Female Sexual Function Inventory (FSFI), confidence to talk with a HCP about vaginal symptoms and sexual health management, plans to implement and implementation of a suggested tip from the intervention materials.

HCP measures

HCP preparedness and confidence in talking to their patients about each of the four reproductive health issues will be measured. Each preparedness item had a 4-point Likert scale response (very unprepared, unprepared, prepared, and very prepared). Each confidence item had a 7-point Likert scale response (not at all confident, slightly confident, somewhat confident, moderately confident, quite confident, very confident, and extremely confident). Demographic, medical specialty, and experience and volume of breast cancer patients, and satisfaction with SCP materials will also be measured.

YBCS participant adherence and retention

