We will deploy several approaches to motivate YBCS participants to complete the study. Participants will receive up to \$100 in Amazon gift cards for completing each of 3 questionnaires and daily hot flash text messages. Weekly, automated reminder emails to complete study tasks will be sent via the web platform. Telephone call and/or text message reminders will be undertaken for overdue tasks for up to 5 contacts. On hot flash text messages, daily reports will be generated to monitor responses and identify those who had not responded in \geq 3 consecutive days for study staff contact.

HCP participant adherence and retention

HCP participants will receive up to \$40 in Amazon gift cards for completing each of 2 questionnaires. Weekly, automated email reminders to complete study tasks and view their patient's SCP will be sent via the website platform. HCPs who opted to participate via paper materials will be contacted by telephone calls to their medical practice to confirm receipt and encourage completion overdue tasks for up to 5 contacts. If a final questionnaire is not received within two months of mailing, questionnaires will be resent.

Statistical Analysis

The primary analysis will be intent-to-treat. The primary composite outcome will be an improvement in at least one reproductive health issue over the 24 week study, defined as: $\geq 50\%$ improvement in enrollment hot flash score, $\geq 50\%$ improvement in enrollment vaginal atrophy symptom score, use of highly effective contraceptive methods (sterilization, long-acting reversible contraception, injectables, pills, patch or vaginal ring), and fertility and pregnancy concern subscale scores <3. Logistic regression models will be used to test for differences by intervention versus control arm; odds ratios with 95% confidence intervals for intervention effect will be reported.

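### Sexual activity after randomization can bring a woman into the contraception analysis set: fix the set at enrollment and say whether it governs the composite

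*Combined protocol and SAP*

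**What the plan says.** In the combined protocol and SAP, the section YBCS outcome measures states: "Contraception outcomes will be analyzed in participants at risk of unintended pregnancy". At risk is "defined as having a uterus and at least one ovary", together with an age limit of 45 and being "sexually active in the 24 months prior to or during the study". No time point is attached to the anatomy or age criteria. The next sentence defines the contraception component of the primary composite, without saying whether the restriction carries over to it.

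The section Statistical Analysis says "The primary analysis will be intent-to-treat", defines the composite as improvement on at least one issue, and assigns the separate contraception comparison to a GEE model. Under Material and Methods, "All participants will be followed for 24 weeks".

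On what each arm receives, the section on intervention development says "The intervention arm will be able to access all 4 sections for all 5 issues"; vaginal symptoms are one of those issues. Controls see only the resource lists. Sexual function, measured by the FSFI, is a secondary outcome. Randomization is stratified by the four issues reported at entry.

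**The concern.** The activity criterion has two limbs joined by *or*. The first looks back from the study and is settled before allocation. The second covers the study itself and, apart from the time between enrollment and randomization (which includes the 7-day run-in), is settled afterwards. A woman with no activity in the preceding 24 months belongs to the set only if the second limb applies to her.

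The trial's own outcomes treat sexual function as something the intervention may improve. If it does, more previously inactive women may enter the contraception denominator in the intervention arm than in the control arm. If their use of highly effective methods differs from that of the other women, the arms can then differ on contraception with no effect on method choice, or a real effect can be partly hidden. Stratification on issues reported at entry cannot balance a set whose membership is decided later.

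There is also a classification gap. A previously inactive woman who leaves without reporting activity can be placed neither in nor out of the set. The planned imputation from the mixed models concerns missing outcomes and gives no rule for missing membership. The plan expects 20% drop-out but does not say how many of these women would have been inactive beforehand.

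**Working it through.** **Plan's own figure.** There is none for this set: no size, usage rate or power is given. The composite power claim (25% against 52%, 50 per arm) recomputes to 80.2%, but it does not bear on this point.

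**Model, with no true effect on method choice.** For each arm:

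rate = [(1 − s)·u_base + s·q·u_new] / [(1 − s) + s·q]

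- s: share of otherwise at-risk women inactive in the 24 months before the study
- q: share of those who become active during the study; may differ by arm
- u_base, u_new: use of a highly effective method among previously active women and new entrants, the same in both arms

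All four are assumptions. u_base is set at 25%.

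**One case in full** (s = 0.30, u_new = 50%):
- Control, q = 0.10: (0.70 × 0.25 + 0.03 × 0.50) / 0.73 = 0.190 / 0.73 = 26.0%
- Intervention, q = 0.40: (0.70 × 0.25 + 0.12 × 0.50) / 0.82 = 0.235 / 0.82 = 28.7%
- Difference: +2.6 points

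| s | q control / intervention | u_new | Control | Intervention | Difference (points) |
|---|---|---|---|---|---|
| 0.15 | 0.10 / 0.20 | 50% | 25.4% | 25.9% | +0.4 |
| 0.15 | 0.10 / 0.40 | 50% | 25.4% | 26.6% | +1.2 |
| 0.30 | 0.10 / 0.40 | 50% | 26.0% | 28.7% | +2.6 |
| 0.15 | 0.10 / 0.20 | 10% | 24.7% | 24.5% | −0.3 |
| 0.15 | 0.10 / 0.40 | 10% | 24.7% | 24.0% | −0.7 |
| 0.30 | 0.10 / 0.40 | 10% | 24.4% | 22.8% | −1.6 |
| 0.30 | 0 / 1 (bound) | 50% | 25.0% | 32.5% | +7.5 |
| 0.30 | 0 / 1 (bound) | 10% | 25.0% | 20.5% | −4.5 |

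The difference is zero if q is the same in both arms or if u_new = u_base.

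**Type I error.** Take 157 × 0.8 / 2 = 62.8, about 63 completers per arm, scale by (1 − s) + s·q, and use a two-sided 5% comparison of two proportions as a stand-in for the GEE. The three non-extreme rows with u_new = 50% give 5.0%, 5.2% and 5.9%. The corresponding bound gives 12.9%.

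**Composite, only if the restriction applies there.** Newly active women gain one more route to improvement. With 25% improving by other routes (the plan's control rate), taken as independent of method use, the added difference is s × (difference in q) × u_new × 0.75:
- 0.15 × 0.10 × 0.50 × 0.75 = 0.6 points
- 0.15 × 0.30 × 0.50 × 0.75 = 1.7 points
- 0.30 × 0.30 × 0.50 × 0.75 = 3.4 points

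These apply to women who meet the anatomy and age criteria. Over all randomized women the addition would be smaller. The plan's design difference for the composite is 52 − 25 = 27 points.

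**Set fixed at enrollment.** q drops out, both arms have expected rate u_base, and the bias from this criterion is zero in the model.

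**The case against.** The case against giving this weight is substantial, and much of it stands.

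- **Few women depend on the second limb.** It matters only for women inactive for two years who become active within 24 weeks. Everyone else is in the set through the look-back limb. A reader might infer that the contraception comparison as a whole no longer compares the randomized arms; the definition does not support that, because membership through the look-back limb is settled before allocation.
- **Drop-outs.** A reader might infer that no drop-out can be classified. Because the limbs are joined by *or*, a woman active beforehand is in the set whether or not she stays. Only previously inactive women who leave without reporting activity are unclassifiable.
- **Intent-to-treat.** A reader might infer a contradiction with the stated principle. That statement covers the primary analysis, and no passage removes women from the composite denominator for not being at risk. Even if the restriction reaches the composite component, the natural reading is that a woman outside the set loses one route to success and stays in her arm. Her endpoint would still depend on post-randomization activity, but she would not be excluded.
- **The size is assumed throughout.** Outside the bounds, type I error barely moves in the cases computed.
- **The second limb has a rationale.** A woman who becomes active during follow-up is then at risk of pregnancy.

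None of this fixes the set before allocation. No section limits it to enrollment data or plans an enrollment-only analysis, so the plan as written would neither reveal nor correct a difference in entry between arms.

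**Conclusion.** The point holds in limited form. Membership of the contraception set depends in part on behavior that is mostly post-randomization and that the intervention could change. The clear target is the secondary GEE comparison. The primary composite is exposed only if the restriction also governs its contraception component, and the outcome measures and Statistical Analysis sections do not settle that. A conflict with intent-to-treat in the primary analysis is therefore not established.

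The likely bias is small and its direction unknown: about −1.6 to +2.6 points in the non-extreme scenarios, and −4.5 to +7.5 at bounds where no previously inactive control woman and every previously inactive intervention woman becomes active. All these figures rest on assumed values of s, q and usage. The scenarios also assume entry is higher in the intervention arm; the signs would reverse if it were lower. The wording defect itself is certain, and since it is cheap to remove, it should be corrected.

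**What to change.** 1. Define the at-risk set from enrollment data only: uterus and ovary status, age 45 or under, and sexual activity within the 24 months before enrollment. Delete the words *or during the study*, and state that all criteria are assessed at enrollment.
2. State whether the restriction applies to the contraception component of the composite. Either way, keep every randomized woman in the composite denominator, in her assigned arm.
3. Keep the present definition as a labelled sensitivity analysis. Report by arm the number of women entering only through study-period activity, and the number who cannot be classified because they left.

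The cost is a few sentences in the plan. Women who become active only after enrollment leave the main contraception set. Under the assumptions above that is s × q of the otherwise at-risk women: 0.15 × 0.10 = 1.5% at the low end, and 0.30 × 0.40 = 12% of the intervention arm in the largest non-extreme scenario. They remain visible in the sensitivity analysis. The enrollment questionnaire must record activity over those 24 months; the documents do not list its items, so this should be confirmed.

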YBCS are eligible if they report experiencing at least one of the four targeted reproductive health issues: hot flashes (\geq 4 per day with \geq 1 at least moderate in severity), moderate to high pregnancy and/or fertility concerns (fertility or pregnancy subscale score >3 on the Reproductive Concerns After Cancer Scale), not using contraception or using a less effective method (barrier or fertility awareness methods, withdrawal, or spermicides), or vaginal atrophy symptoms (\geq 1 symptom of vaginal dryness, irritation, soreness or dyspareunia over the past 4 weeks reported as at least moderate in severity). Additional eligibility criteria include: ages 18-50 at study enrollment, diagnosed with stage 0-III breast cancer between ages 18-45, completed primary cancer treatment including surgery, chemotherapy and radiation, are not pregnant at enrollment, are able to read English and access the Internet, and are able to complete daily text message hot flash diaries.

YBCS are recruited from the following sources: (1) cancer advocacy organizations including the Young Survival Coalition, Susan G. Komen San Diego and Army of Women-a program by the [name] Research Foundation, (2) referrals from health care providers and patient advocates, (3) Research Match, (4) previous observational studies conducted by the investigators. Interested YBCS are directed to the study web portal to create a secure personal account, followed by online access to study description, screening for eligibility and consent.

Consented participants complete the enrollment questionnaire and undergo a 7-day daily hot flash text message run-in period. Participants receive two daily text messages prompting them to report the number of hot flashes and severity of each hot flash (mild, moderate, severe, or very severe) in the previous 24 hours. Participants with at least 70% adherence over 7 days are then randomized.

YBCS randomization

Computerized, blocked randomization with equal allocation to intervention and waitlist control arms was undertaken. Randomization is stratified by the four a priori reproductive health issues in order to

maintain balance between the intervention and waitlist control groups with regard to these factors. Fifteen unique strata were created based on possible combinations of experiencing one or more of the four late effects.

HCP eligibility, recruitment, consent, enrollment and procedures

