Hot flash frequency and severity over the prior 24 hours will be measured in each questionnaire and via daily via text messages using the following questions: "How many hot flashes have you had in the past 24 hours?" and "How many of your hot flashes in the past 24 hours would you categorize as mild, moderate, severe and/or very severe?" The hot flash score is calculated as the weighted sum of the number of hot flashes in each severity category multiplied by a severity-exclusive weight (1-mild, 2-moderate, 3-severe, 4-very severe). For the primary analysis, a decrease of 50% in the hot flash score will be defined as an improvement in hot flashes for the primary composite outcome. Secondary hot flash outcomes will include quality of life measured by the 29-item Menopause-specific Quality of Life (MENQOL) scale, confidence to talk with a HCP about hot flash management, plans to implement and implementation of a suggested tip from the intervention materials.

Fertility-related concerns will be measured with the Reproductive Concerns After Cancer Scale (RCAC), specifically fertility potential and pregnancy subscales. The RCAC is an 18-item multidimensional scale composed of 6 subscales (fertility potential, pregnancy, child's health, disclosure to partner of fertility status, personal health, acceptance of infertility) measuring reproductive health concerns of young adult female cancer survivors. The two subscales were chosen, because the SCP-R content addressed these constructs. Each subscale consists of 3 questions with response options ranging from 1 "Strongly disagree" to 3 "Neither agree nor

disagree" to 5 "Strongly agree". Scores for the fertility and pregnancy subscales will be calculated by averaging responses (range 1-5), scores > 3 indicating concern. For the primary analysis, scores \leq 3 in follow up will be considered an improvement in fertility-related concerns for the primary composite outcome. Secondary fertility-related outcomes will include the overall RCAC score, referral, consultation and treatment with a fertility specialist, pregnancy planning, and confidence to talk with a HCP about fertility-related concerns and plans to implement and implementation of suggestions from the fertility SCP.

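### The primary 50% hot-flash responder rule names no score source, averaging window or deciding visit, and its wording leans towards noisy single-day reports although daily diaries are collected

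*Combined protocol and SAP*

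**What the plan says.** The hot flash outcome section scores a 24-hour report by weighting each flash 1 to 4 for severity. It gives the score two sources: frequency and severity "over the prior 24 hours will be measured in each questionnaire and via daily via text messages". For the composite, "a decrease of 50% in the hot flash score will be defined as an improvement in hot flashes".

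The Statistical Analysis section anchors the rule to a 50% or greater "improvement in enrollment hot flash score" and frames the composite as "improvement in at least one reproductive health issue over the 24 week study". It places participant responses at enrollment, 12 and 24 weeks, in the paragraph on the secondary models.

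Diary data will exist before and after randomization. On eligibility and enrollment: "Consented participants complete the enrollment questionnaire and undergo a 7-day daily hot flash text message run-in period", and "Participants with at least 70% adherence over 7 days are then randomized". Under Material and Methods, all participants "report daily hot flash frequency and severity via text messaging, and complete a 12-week and a final 24-week questionnaire". The section on the website and text messaging gives the reason for the diary: "Daily hot flash text messages will provide near real-time data collection to minimize recall bias".

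The Sample size section assumes an SD of change of 5 score units per patient per day. It states 80% power for 25% versus 52% on the composite, in a calculation with 50 per arm.

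**The concern.** Three things needed to compute this component are open: the source, the number of days averaged at each end, and the visit that decides. Week 24 alone, week 12 or 24, or any time in follow-up would all fit the composite's time frame. Each choice labels different women as responders, and nothing in the text prevents the choice being made after data are seen.

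The choice also affects quality. A 50% drop between two single days mixes real change with day-to-day variation. An unchanged woman who enrolls on a bad day and reports on a good one counts as a success. This can happen in either arm, so it adds the same kind of noise to both and pulls their response rates together. Hot flashes are one of four routes to the composite, so the dilution reaches the primary test in proportion to how many women depend on that route.

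**Working it through.** **The plan's own figure.** A two-sided pooled two-proportion test at alpha 0.05, with 50 per arm and 25% versus 52%, gives 80.2% power. The stated 80% reproduces.

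**Inputs.** From the documents: SD of change 5 score units; responder cut 50%; lowest score that meets the hot-flash entry criterion = 3 mild + 1 moderate = 3×1 + 1×2 = 5. Assumed, because the documents do not give them: true mean daily score μ = 6, 8 or 10; normally distributed daily scores; share s of the change variance that is daily noise; 30% of daily variance shared within a week; one deciding visit; no true change.

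**Formula.** With daily variance V, the change between two single days has variance 2V, so V = s × 25/2. For baseline B and follow-up F with common mean μ, F − 0.5B has mean 0.5μ and variance V + 0.25V = 1.25V. Hence P(F ≤ 0.5B) = Φ(−0.5μ/√(1.25V)). For 7-day means, V is replaced by V × (0.3 + 0.7/7) = 0.4V, or by V/7 if days are independent.

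Worked case, s = 1, μ = 6:
- Single days: V = 12.5, √(1.25 × 12.5) = 3.953, Φ(−3/3.953) = 0.224.
- 7-day means, 30% shared: 0.4V = 5, √(1.25 × 5) = 2.5, Φ(−3/2.5) = 0.115.

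| Chance of a ≥50% drop, no true change | μ = 6 | μ = 8 | μ = 10 |
|---|---|---|---|
| s = 1, single days | 22% | 16% | 10% |
| s = 1, 7-day means, 30% shared | 12% | 6% | 2% |
| s = 1, 7-day means, independent days | 2.2% | 0.4% | 0.04% |
| s = 0.5, single days | 14% | 8% | 4% |
| s = 0.5, 7-day means, 30% shared | 4% | 1% | 0.2% |
| s = 0.25, single days | 6% | 2% | 0.6% |

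**Why the s = 1 row is not a ceiling.**
- The SD of 5 is not tied to one-day or averaged scores. If it describes 7-day means with 30% shared, V = 12.5/0.4 = 31.25, and the single-day chance is 32/26/21%.
- The table ignores the entry screen. If the enrollment report that serves as baseline must itself be at least 5, the s = 1 single-day figures become about 30/18/11%, through regression to the mean.
- A separate count simulation with the full hot-flash entry criterion and independent days gave 15% to 43% for single days and 0.3% to 5% for 7-day means. It assumed mean counts of 4 to 8 per day, Poisson or overdispersed days, and a severity mix of 35/40/20/5%.

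**Effect on the composite.** Let h be the share of women whose outcome the hot-flash item can decide and f the chance response. If 25% and 52% are rates without chance responders, and no true responder is missed, control becomes 0.25 + 0.75hf and intervention 0.52 + 0.48hf. The difference is 0.27(1 − hf). With assumed h = 0.5 and f = 0.224 it is 0.27 × 0.888 = 0.240, and power at 50 per arm is 68%. With f = 0.115 it is 0.27 × 0.9425 = 0.254, and power is 74%. If 25% and 52% already include chance responders, there is no loss against the stated power.

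**Cost in diary data.** If days are answered independently with probability 70/80/90%, the binomial chance of fewer than 5 of 7 days is 35/15/3%, and of fewer than 4 of 7 is 13/3/0.3%. A 4-day mean loses little: the variance is V(0.3 + 0.7/4) = 0.475V, which at s = 1 gives 13/7/3% against 12/6/2% for seven days.

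**The case against.** The strongest reply is that the source is not really open. The rule is tied to the enrollment score, the document names an enrollment questionnaire, it calls the diary week a run-in, and the listed measurement times match the three questionnaires. Much of this stands: the two readings are not equally supported, and the text favors the questionnaire. But that is the single-day reading, so the reply makes the noise problem more likely. It also leaves the deciding visit unstated. A reader might go further and infer that the plan does use single-day scores. The documents do not say so: the run-in diary also precedes randomization, and the texts run throughout follow-up.

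A second reply is that the sizes rest on stacked assumptions. This is correct. Mean score, daily variance, within-week sharing and the hot-flash share are all absent from the documents, and the count simulation gives larger effects than the normal model. The figures illustrate; they do not estimate.

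A third reply is that power may not suffer at all. The Sample size section speaks only of participants who improve, without setting chance improvement aside, so observed rates are a natural reading of 25% and 52%. This also stands.

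A fourth reply is that replacing the enrollment questionnaire by diary means redefines a primary component if the questionnaire was intended. That is true and should be acknowledged in the change.

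**Conclusion.** The specification gap is real and needs no assumption: source, window and deciding visit are not stated for a component of the primary composite. The gain from averaging is conditional. If the SD of 5 is all single-day noise and 30% of daily variance is shared within a week, chance response falls from about 22/16/10% to about 12/6/2% at mean scores of 6/8/10. It starts lower if less of that SD is daily noise, and higher if the SD refers to averaged scores or the entry screen acts on the baseline report.

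Three stronger readings are tempting and not supported:
- *That the trial is biased or its type I error inflated by this noise.* Under no effect, chance response is the same in both arms.
- *That 22/16/10% is a worst case.* The documents do not say what the SD of 5 measures.
- *That the trial is underpowered.* The 68% above holds only if 25% and 52% exclude chance responders and the assumed inputs hold.

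This should be changed, with medium confidence about the size of the benefit.

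**What to change.** State the rule in full:
- Baseline: mean daily hot flash score over the 7-day run-in.
- Follow-up: mean daily score over the 7 diary days ending at one named deciding visit.
- Minimum: a stated number of diary days, for example 4 or 5 of 7. The run-in threshold of 70% corresponds to 4.9 of 7 days, so most baselines should meet it.
- Below the minimum: treat the component as missing and use the imputation already planned from the mixed models, fitted to the same score.
- Sensitivity analysis: the single-day questionnaire score.

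Do not use the questionnaire score as a fallback in the primary analysis. A one-day follow-up against a 7-day baseline leaves about 21/14/9% chance response (s = 1, 30% shared), against 12/6/2% with full diaries. Chance response would then depend on diary adherence. Adherence could differ by arm, because controls receive study-adherence texts and the intervention arm receives reproductive health prompts.

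Also say which kind of score the SD of 5 describes, and whether 25% and 52% include chance improvement.

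The cost is wording, since the diary data are already collected. If questionnaire scores were intended, it is also a change to a primary component, to be made before outcome data are seen. The main downside is missing values: about 35/15/3% of women would fall below 5 of 7 days at assumed daily response of 70/80/90%, or 13/3/0.3% below 4 of 7. Diary completeness should be reported by arm.
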